## Evaluation of Drug-Induced Serious Hepatotoxicity

The evaluation of drug-induced serious hepatotoxicity (eDISH) will be based on a tabulation by subject number [Table 14.3.4.3] and scatter plot figure. The table will present all scheduled and unscheduled ALT, AST, ALP and TBL of any patient with AST or ALT > 3x ULN or TBL > 2 x ULN. This table will be assessed to identify any incidence of

1. Three-fold or greater elevations above the ULN of ALT or AST and
2. Among patients showing such AT elevations, any patient with elevation of serum TBL to >2xULN and without initial finding of cholestasis (elevated serum ALP).

Side by side scatter plots will be presented of time-matched ALT versus TBL [Figure 14.3.1.1] and time-matched AST versus TBL [Figure 14.3.1.2] grouped to combined TS-121 treatment

# Statistical Analysis Plan

Taisho Pharmaceutical R&D Inc.  
Protocol TS121-US201

Statistical Analysis Plan (SAP)

Final 2.0  
18 Dec 2018  
CONFIDENTIAL

groups and placebo. These plots will be presented using  $\times$ ULN units and logarithmic scale. The ALT versus TBL and AST versus TBL plots will also be presented using each patient's post-baseline maximum value [Figure 14.3.2.1 and Figure 14.3.2.2].

### **6.3.16.3 Vital Signs**

Vital signs will be listed [Listing 16.2.9.1.1]. Vital signs change from baseline will also be listed [Listing 16.2.9.1.2]. Baseline is defined as the scheduled predose assessment of Visit 3. Only if scheduled Visit 3 result is missing, will the latest predose assessment be used as the baseline for that subject number and test. Change from baseline will be calculated only for vital signs evaluated post-baseline and with at least one recorded pre-dose assessment.

Descriptive summaries (n, mean, SD, SE, CV%, minimum, median and maximum) of vital signs (by parameter) and oral body temperature measurements observed values and change from baseline will be presented by treatment and time point [Table 14.3.6.1.1 and Table 14.3.6.1.2].

### **6.3.16.4 12-Lead Electrocardiogram**

Electrocardiogram data (ventricular rate, RR, PR, QT, QTcB and QTcF interval data, QRS duration) will be listed [Listing 16.2.9.2.1] with the Investigator interpretation. Any QTcF or QTcB  $>500$  msec will be flagged in the listing. Electrocardiogram data change from baseline will be listed [Listing 16.2.9.2.2] and each flagged to distinguish QTc change from baseline 30 to 60 msec or  $>60$  msec.

Descriptive summaries (n, mean, SD, SE, CV%, minimum, median and maximum) of interval data observed values and change from baseline will be presented by treatment and time point [Table 14.3.6.2.1 and Table 14.3.6.2.2]. Baseline is defined as the scheduled predose assessment of Visit 3. Only if scheduled Visit 3 result is missing, will the latest predose assessment be used as the baseline for that subject number and test.

The categorical analysis of QTcB and QTcF will be presented in a frequency table of patients categorized based on maximum post-baseline QTc ( $\leq 500$  msec or  $>500$  msec) and maximum change from baseline ( $<30$  msec, 30 to 60 msec, and  $>60$  msec) [Table 14.3.6.2.3].

The incidence of abnormalities, based on the clinical interpretations from the Investigator, will be enumerated by treatment group and visit [Table 14.3.6.2.4].

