 13. Patients who are undergoing treatment with drugs that might influence HPA axis function, including psychotropic medications, benzodiazepines, metyrapone, lithium and/or corticosteroids
[Please refer to Section 8.3 for a more detailed list of prohibited concomitant medications]
 14. Patients who need/plan to take moderate to strong CYP3A4 inhibitors/inducers (food, beverages, medications and supplements) during this study (see Appendix 1)
 15. Patients who work night shifts or need to work night shifts during the trial
 16. Females who are pregnant, intend to become pregnant (within 90 days of the last dose), or who are breastfeeding
 17. Patients with significant hepatic, renal, cardiovascular, hemodynamic, pulmonary, gastrointestinal, hematological, locomotor, immunologic, ophthalmologic, metabolic, neurological, or endocrine disease that in the opinion of the investigator would confound participation or study results

18. Patients with clinically significant ECG* findings at Visit 1 or Visit 3, or hematology, biochemistry, or urinalysis abnormalities at Visit 1 (abnormal laboratory values considered to be not clinically significant as per the investigator are acceptable)
[* Note: QTcF interval of > 450 msec in males or > 470 msec in females, will be the basis for exclusion from the study; ECG may be repeated once for confirmatory purposes, if an initial value is obtained that exceeds the values specified]
19. Patients with history or presence of cataract (lens opacities with vision disturbances), glaucoma, chronic inflammatory eye disease, significant eye trauma, any ophthalmic surgical procedure (e.g. cataract or glaucoma) or any ocular laser surgery in either eye
20. Patients with lens opacity based on ophthalmological examination performed at Visit 2 as listed below:
- Nuclear opalescence (NO) with a LOCSIII classification > 3.0 in either eye
 - Nuclear color (NC) with a LOCSIII classification > 3.5 in either eye
 - Cortical lens opacities (C) with a LOCSIII classification > 2.0 in either eye
 - Posterior subcapsular lens opacities (P) with a LOCSIII classification > 0.3 in either eye
21. Patients with a history (within 5 years) or presence of malignancy at Visit 1
[Note: History (within 5 years) of non-metastatic, non-progressive basal and/or squamous cell carcinoma of the skin, in situ cervical and prostate cancer are exceptions (currently in remission)]

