# Statistical Analysis Plan

Taisho Pharmaceutical R&D Inc.  
Protocol TS121-US201

Statistical Analysis Plan (SAP)

Final 2.0  
18 Dec 2018  
CONFIDENTIAL

median and maximum) will be calculated for each quantitative variable (unless otherwise stated).

All statistical programming will use SDTM data and will be based on SDTM mapping rules for scheduled, unscheduled and repeat visits. No assessment or exclusions other than the mapping specifications will be performed for visits out of the planned visit window.

Listings will include repeat and unscheduled measurements.

The following rules will apply to repeat and unscheduled measurements in summary tables:

- No more than one assessment per patient per time point will be used in the summary of each scheduled safety or efficacy endpoint.
- If the repeated measurement occurs prior to the first dose of study drug for the treatment period, then the last obtained value of any repeated measurement will be used as baseline in the summary tables.
- If the repeated measurement occurs after the first dose of study drug for the treatment period, then the first obtained value of any repeated measurements will be used in the summary tables.

Unless specified otherwise, the baseline used for any change from baseline measurements will be the last measurement prior to the first dose of study drug for the treatment period.

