## ***6.3.16.2 Clinical Safety Laboratory Tests (Biochemistry, Hematology and Urinalysis)***

Clinical laboratory biochemistry and hematology results will be presented, using conventional units (original units, received from the laboratory are consistent with CDISC standards) and standard international (SI) units, will be listed by subject number and study time point [Listing 16.2.8.1.1 through Listing 16.2.8.2.2]. Laboratory analyses will utilize scheduled Visit 3 assessments as baseline values. Only if scheduled Visit 3 result is missing will the latest predose assessment be used as the baseline for that patient and test. Change from baseline will be calculated only for laboratory tests with at least one recorded pre-dose assessment.

Certain hematology test samples were assessed by certain sites’ local laboratory and these will be listed together with the corresponding central laboratory results.

Clinical urinalysis and urinalysis microscopic tests will be listed using conventional units [Listing 16.2.8.3].

Laboratory reference ranges, in conventional and SI units will be listed [Listing 16.2.8.4].

All values outside the clinical reference ranges will be flagged in the data listings. The quantitative abnormal values will be flagged with ‘L’ for values below the lower limit of the clinical reference range and ‘H’ for values above the upper limit of the clinical reference range and included in the listings. In addition, certain qualitative tests may be flagged abnormal ‘A’. The Investigator will assess whether the values outside the clinical reference range are clinically significant and laboratory values outside the reference ranges will be reported as abnormal not clinically significant (NCS) or abnormal clinically significant (CS). Clinically significant laboratory values will be recorded by the Investigator as AEs.

Abnormal laboratory values ordered by test category (biochemistry, hematology and urinalysis), randomized treatment, subject number, laboratory test, date and time will be listed using conventional and SI units [Listing 16.2.8.5.1 and Listing 16.2.8.5.2]. Abnormal CS

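### SAP 6.3.1 and 6.3.16.4 give conflicting baselines for a repeated Visit 3 ECG; read literally, 6.3.16.4 understates QTc change for any patient randomized on a confirmatory QTcF

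*SAP*

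**What the plan says.** Two places in the SAP set the baseline for the same summary tables.

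- **SAP 6.3.1 (Listings and Descriptive Statistics).** Where a measurement is repeated before the first treatment-period dose, "the last obtained value of any repeated measurement will be used as baseline in the summary tables". That bullet carries no exception. A separate sentence gives the general definition: "Unless specified otherwise, the baseline used for any change from baseline measurements will be the last measurement prior to the first dose of study drug". The section leaves the sorting of records to programming that is "based on SDTM mapping rules for scheduled, unscheduled and repeat visits".
- **SAP 6.3.16.4 (12-Lead Electrocardiogram).** "Baseline is defined as the scheduled predose assessment of Visit 3". It continues: "Only if scheduled Visit 3 result is missing, will the latest predose assessment be used as the baseline for that subject number and test".

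SAP 6.3.16.3 (vital signs) and 6.3.16.5 (body weight) have the same rule as the ECG section. SAP 6.3.16.2 (laboratory tests) has it in nearly the same words: "Only if scheduled Visit 3 result is missing will the latest predose assessment be used as the baseline for that patient and test".

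Protocol 7.1.2, exclusion 18, makes the QTcF at Visit 1 or Visit 3 a ground for exclusion above 450 msec in men and 470 msec in women. It adds that the "ECG may be repeated once for confirmatory purposes, if an initial value is obtained that exceeds the values specified". Under footnote e of the schedule in Protocol 9.1, randomized dosing starts the morning after Visit 3, so a repeat taken on the Visit 3 day is pre-dose.

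**The concern.** Suppose a patient's Visit 3 ECG is over the limit, is repeated the same day and passes. The bullet in 6.3.1 makes the repeat the baseline. Section 6.3.16.4, read literally, keeps the scheduled reading, because that reading is not missing. A programmer cannot follow both.

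The choice matters because such repeats are not random. The protocol allows one only after a high first value, so the scheduled reading of a patient who is then randomized is selected for being high. Measured from it, later change looks smaller. The outputs exposed are the ECG change-from-baseline summaries and listing, and the maximum-change categories (<30, 30 to 60, >60 msec) in Table 14.3.6.2.3. Protocol 4.4.3 reports treatment-emergent ventricular arrhythmias with this drug, and in a trial of about 180 patients such categories may rest on very few people. One or two reclassified patients could change how the table reads.

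**Working it through.** The documents give no figure for this point and no QTcF distribution. The direction of the error follows from the rules alone; its size needs assumptions.

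**Step 1: direction.** Let S be the scheduled Visit 3 QTcF, R the repeat, L the limit (450 or 470) and M the maximum post-baseline QTcF. A repeat requires S > L. Randomization on the repeat requires R ≤ L. So S − R > 0 in every such patient. Change from the scheduled value is M − S and from the repeat M − R; the shortfall is (M − R) − (M − S) = S − R, always positive.

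**Step 2: two illustrative men (invented values).**
- S = 458, R = 440, M = 478. Change: 478 − 458 = 20 msec (<30) from the scheduled value, against 478 − 440 = 38 msec (30 to 60) from the repeat.
- S = 470, R = 445, M = 506. Change: 506 − 470 = 36 msec (30 to 60), against 506 − 445 = 61 msec (>60). The >500 msec flag is raised either way, because it does not use baseline.

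**Step 3: how many, and how far off.** Simulation with assumed normal QTcF: mean 405 to 425 msec, between-patient SD 15 to 18, within-patient SD 8 to 12. A patient is affected if the first reading is above the limit and the repeat at or below it.
- Share affected: almost none at the 470 limit with the low means, rising to about 6% at the 450 limit with mean 425 and SDs 18 and 12 (0.06 × 180 ≈ 11 if all 180 faced that limit). That extreme is about 6.8% if the Visit 1 ECG screen is ignored; the screen lowers the counts by roughly 5-18%.
- In affected patients, the scheduled value overstates true baseline by about 9 to 28 msec on average. The repeat understates it by about 1 to 7 msec.

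**Step 4: effect on the SAP's category.** Table 14.3.6.2.3 uses the maximum change, so take the largest of three post-baseline ECGs and assume a true shift of 35 msec. The chance of reaching 30 msec is:
- from the scheduled value, about 17-61%;
- from the repeat, about 88-98%;
- from the true baseline, 1 − Φ(−5/w)³ with w the within-patient SD. For w = 8 this is 1 − 0.266³ ≈ 98%, and for w = 12 it is 1 − 0.338³ ≈ 96%.

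**Step 5: a smaller shift.** A separate run used means of 410 (men) and 420 (women), between-patient SD 15 to 20, within-patient SD 6 to 14, and the Visit 1 screen. With a true shift of 20 msec, 0.5-9.5% of affected patients reach 30 msec from the scheduled value and 32-67% from the repeat. The expected number affected was 0.6 to 5.3 per 180 if all were men and 0.1 to 2.4 if all were women.

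**The case against.** The strongest reply is that the sections can be read together. The SAP says 'scheduled', not 'first'. Section 6.3.16.4 may only choose the visit (Visit 3 before any earlier one), leaving 6.3.1 to choose the last reading within it. The mapping rules that classify repeats are not in these documents, and the general baseline sentence in 6.3.1 expressly yields to section-specific rules. This stands to the extent that nobody can state as fact that the over-limit value will be used. It does not remove the conflict. The repeat bullet in 6.3.1 has no such exception, and 6.3.16.4 contrasts the scheduled result with the latest pre-dose one, which is what a Visit 3 repeat is.

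Four other objections stand and limit the point.

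- A reader might infer that QTc prolongation as a whole is understated. The documents do not support that: maximum post-baseline QTc, the >500 msec count and the investigator's interpretation do not use baseline, and repeats are kept in the listings.
- A reader might infer the same one-way bias for laboratory tests. Laboratory eligibility is judged at Visit 1, and Protocol 9.2.7.8 allows repeats at the investigator's discretion with no fixed direction. A suspect Visit 3 value kept as baseline could distort the Appendix B ratios either way.
- The problem arises before randomization and applies to every arm, so it favours none by design. It does attenuate change wherever a real increase exists.
- The repeat is not a perfect baseline. In the Step 5 run with no drug effect, the chance of a maximum change of 30 msec or more was at most 0.4% from the scheduled value, but ranged from close to zero to about 20% from the repeat, the top figure at a within-patient SD of 14. This is a reason to show both values, not to keep the over-limit one.

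**Conclusion.** The SAP states two baseline rules that cannot both be applied to a repeated Visit 3 ECG. On the literal reading of 6.3.16.4, change from baseline is understated by exactly S − R for each patient randomized on a confirmatory Visit 3 QTcF. That direction needs no assumption beyond exclusion 18.

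The size does. The number affected is small, and the shift in classification within that group is large. The figures rest on assumed normal distributions, and the 35 msec shift is illustrative: it sits just above the 30 msec cut, and nothing in the documents suggests an effect of that size. Protocol 4.4.3 describes arrhythmias, not QTc prolongation. The contrast remains at 20 msec.

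The conclusion is confined to ECG change-from-baseline outputs. It is a conflict to be resolved in the text, not a demonstration that the trial's QTc results will be wrong.

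**What to change.** Before database lock:

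1. In SAP 6.3.16.4, state that when the Visit 3 ECG is repeated before the first randomized dose, baseline is the last valid pre-dose Visit 3 value, as 6.3.1 already provides. If Visit 3 is missing, use the latest earlier pre-dose value.
2. For patients with a repeated Visit 3 ECG, show change from both the scheduled value and the repeat, so that any dependence of the 30 to 60 and >60 msec counts on the choice is visible.
3. Align the wording in 6.3.16.2 (laboratory) with the same rule, without claiming a one-directional bias there. Do the same in 6.3.16.3 (vital signs) and 6.3.16.5 (body weight) for consistency only.

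The cost is about one sentence in each of four subsections and a short supplementary display. No new data are needed.

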# Statistical Analysis Plan

Taisho Pharmaceutical R&D Inc.  
Protocol TS121-US201

Statistical Analysis Plan (SAP)

Final 2.0  
18 Dec 2018  
CONFIDENTIAL

## **6.3.16.5 Body Weight**

All body weight (kg) measurements and change from baseline will be listed [Listing 16.2.9.3]. Descriptive summaries (n, mean, SD, SE, CV%, minimum, median and maximum) of body weight and change from baseline will be presented by treatment and time point [Table 14.3.6.3.1 and Table 14.3.6.3.2]. Baseline is defined as the scheduled predose assessment of Visit 3. Only if scheduled Visit 3 result is missing, will the latest predose assessment be used as the baseline for that subject number and test.

## **6.3.16.6 Ophthalmological Examinations**

The observed and change from baseline LOCS III grading scores and best corrected visual acuity scores will be listed [Listing 16.2.9.4]. Any LOCS III grade increase from baseline  $\geq 0.5$  or  $\geq 0.8$  will be flagged. The flagged records will also be interpreted and annotated based on the definition of Class I lens event [increase from baseline in the LOCS III grade of  $\geq 0.5$  (Nuclear Opalescence),  $\geq 0.8$  (Cortical) or  $\geq 0.5$  (Posterior Subcapsular)]. Any record of Class I lens events will be listed [Table 14.3.6.4.1].

Descriptive statistics (n, mean, SD, SE, CV%, minimum, median and maximum) of LOCS III grading items and best corrected visual acuity score and change from baseline will be presented by treatment and time point [Table 14.3.6.4.2 and Table 14.3.6.4.3]. Baseline is defined as the latest predose assessment of Visit 2.

## **6.3.16.7 Columbia Suicidal Severity Rating Scale (C-SSRS)**

Responses to C-SSRS suicidal ideation questions 1 through 5, the suicidal ideation score and score change from baseline will be listed by treatment, subject number and visit [Listing 16.2.9.5.1]. All reported responses to Suicidal Ideation Item 1 (Wish to be dead) and Item 2 (Non-Specific Active Suicidal Thoughts), any positive response to Item 3 Item 4 Item 5 and the suicidal ideation score with change from baseline will be listed.

A shift table of suicidal ideation items 1 and 2 evaluated at baseline (Visit 3) and at Week 2, Week 4, Week 6/EOT, and Follow-up will be presented [Table 14.3.6.5.1]. A descriptive summary (n, mean, SD, SE, min, median, max) by treatment and visit will be presented of observed and change from baseline suicidal ideation score [Table 14.3.6.5.2].

The suicidal ideation intensity rating, including rating 0, any reported intensity of suicidal ideation and any reported suicidal behavior will be listed [Listing 16.2.9.5.2].

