7.1.2 Exclusion Criteria

Patients are to be excluded from study participation if they meet any of the following exclusion criteria:

1. Patients with first episode of depression >60 years of age
2. Patients with inadequate response to ≥ 2 prior antidepressant treatments (not including current antidepressant) of at least 4 weeks duration each for the current episode at Visit 1 (to be confirmed at Visit 1.1 by the central rater using MGH ATRQ)
3. Patients whose current depressive episode is diagnosed with psychotic features, catatonic features, post-partum (primary onset), or is secondary to a general medical disorder
4. Patients with a diagnosis of any of the following DSM-5 class disorders
 - Schizophrenia spectrum and other psychotic disorders
 - Bipolar and related disorders
 - Anxiety disorders

[Note: Co-morbid generalized anxiety disorder and social anxiety disorder will be allowed in the study if the primary diagnosis is MDD, and if in the opinion of the

- investigator, the comorbid anxiety is not likely to interfere with the subject's ability to participate in the trial or affect study outcome]
- Obsessive-compulsive and related disorders
 - Trauma- and Stressor-related disorders
5. Patients who received electroconvulsive therapy (ECT) within 12 months of Visit 1, received more than one course of ECT in their lifetime or plan to receive ECT during the study
 6. Patients who received repetitive transcranial magnetic stimulation (rTMS) within 12 months of Visit 1 (Screening) or plan to receive rTMS during the study
 7. Patients who plan to initiate or terminate cognitive or behavioral psychotherapy or alter the frequency of ongoing therapy during this study
 8. Patients who have attempted suicide within the past 6 months
 9. Patients who have a C-SSRS suicidal ideation score of 5 or "yes" response for any of the C-SSRS suicidal behavior questions at Visit 1 or Visit 3
 10. Patients with history or presence of intellectual disability, pervasive developmental disorder, cognitive disorder, neurodegenerative disorder (e.g., Alzheimer disease, Parkinson disease, multiple sclerosis, Huntington disease), or brain injury
 11. Patients with any history or complication of convulsive disorder (e.g., epilepsy)
 12. Patients with history or presence of medical conditions associated with HPA dysfunction (e.g., Cushing syndrome)

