11.3.1 Suicidal Ideation and Behavior

Any patient who, based on the investigator's judgment, poses an imminent risk of suicide, as suggested by the C-SSRS suicidal ideation score of 5 or any "yes" response for any of the C-

SSRS suicidal behavior questions should be discontinued from the study (see Section 8.5). Suicidal ideation or behavior should be recorded as AE and reported to [REDACTED] within 24 hours of becoming aware of the event whether or not the event is considered an SAE or deemed to be related to investigational product. All efforts should be taken to minimize the risk of suicide and the investigator should carefully monitor the patient. Any patients who show evidence of suicidal behavior during the course of the study should be evaluated immediately and/or referred to their attending psychiatrist or to a local emergency room etc. so the patient can receive an appropriate care. The site should have the ability to direct any patient who requires emergency hospitalization to an emergency room or inpatient psychiatric unit. In addition, 24 hour contact information to site personnel should be provided to all patients should they have serious worsening of their condition.

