# Statistical Analysis Plan

Taisho Pharmaceutical R&D Inc.  
Protocol TS121-US201

Statistical Analysis Plan (SAP)

Final 2.0  
18 Dec 2018  
CONFIDENTIAL

The suicidal ideation score is calculated as the maximum score of responses to the first 5 questions.

- Wish to be dead (positive response is scored 1)
- Non-specific active suicidal thoughts (positive response is scored 2)
- Active suicidal ideation with any methods (not plan) without intent to act (positive response is scored 3)
- Active suicidal ideation with some intent to act, without specific plan (positive response is scored 4)
- Active suicidal ideation with specific plan and intent (positive response is scored 5)

The suicidal ideation score will be set Not Applicable (numeric score = 0) when Item 1 and Item 2 responses are negative. An EOCS for suicidal ideation and behavior, as defined in CSP Section 11.3.1, may be recorded for any patient who has a C-SSRS suicidal ideation score of 5 or a “yes” response for any of the C-SSRS suicidal behavior questions.

The suicidal ideation intensity rating will be calculated as the sum of numbers endorsed on 5 intensity items (Frequency, Duration, Controllability, Deterrents and Reasons for Ideation).

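### The only C-SSRS shift table covers ideation items 1 and 2, so the SAP gives no by-arm count, derived from the C-SSRS data, of worsened ideation, worst category or suicidal behaviour

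*SAP*

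**What the plan says.** SAP 6.3.16.7 plans two C-SSRS tables and two listings.

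- Table 14.3.6.5.1 is "A shift table of suicidal ideation items 1 and 2 evaluated at baseline (Visit 3") and at Week 2, Week 4, Week 6/EOT and Follow-up. Items 3 to 5 and behaviour are not in it.
- Table 14.3.6.5.2 gives n, mean, SD, SE, minimum, median and maximum of the ideation score and its change from baseline, by treatment and visit.
- Listing 16.2.9.5.1 carries the ideation items, the score and its change. Listing 16.2.9.5.2 carries intensity and any reported behaviour.

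SAP 6.1.3.8 defines the score: "The suicidal ideation score is calculated as the maximum score of responses to the first 5 questions". The scale runs from 0 through "Non-specific active suicidal thoughts (positive response is scored 2") to "Active suicidal ideation with specific plan and intent (positive response is scored 5"). The same section says that an EOCS "may be recorded for any patient who has a C-SSRS suicidal ideation score of 5" or a positive behaviour question.

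Protocol 7.1.2 (criterion 9) excludes "Patients who have a C-SSRS suicidal ideation score of 5" or any positive behaviour question at Visit 1 or Visit 3. Criterion 8 separately excludes a suicide attempt in the past 6 months. Protocol 11.3.1 adds: "Suicidal ideation or behavior should be recorded as AE". Protocol 10.5.1.6 asks only that emergent ideation or behaviour be listed and leaves further detail to the SAP.

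**The concern.** A shift table is where a reader looks to see how many patients in each arm got worse. This one stops at the two mildest ideation items. A patient who already has non-specific active thoughts at baseline and later reports a plan with intent can occupy the same cell at both times. A patient with new suicidal behaviour need not move at all.

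Suicidal ideation and behaviour is one of only two EOCS categories in Protocol 11.3, and a primary objective in both documents is safety compared with placebo. That comparison needs patients counted by arm.

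**Working it through.** The documents give no figure to reproduce, so the check is an enumeration of what the shift table can show.

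**Inputs**
- Permitted baseline scores: 0 to 4 (Protocol 7.1.2, criterion 9).
- Possible post-baseline scores: 0 to 5 (SAP 6.1.3.8).
- Table content: items 1 and 2 only (SAP 6.3.16.7).
- Planned arm size: 60 (Protocol synopsis).
- Assumption, not stated in the documents: item 1 is positive at any score of 1 or more, and item 2 at any score of 2 or more. SAP 6.1.3.8 supports part of this, because it sets the score to 0 when items 1 and 2 are both negative. A positive score therefore needs at least one of them.

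**Step 1. All worsenings.** From baselines 0, 1, 2, 3 and 4 there are 5 + 4 + 3 + 2 + 1 = 15 upward moves.

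**Step 2. Moves that leave items 1 and 2 unchanged.** These are the moves from a baseline of 2 or more: 2 to 3, 2 to 4, 2 to 5, 3 to 4, 3 to 5 and 4 to 5. That is 3 + 2 + 1 = 6 of 15.

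**Step 3. What the other 15 − 6 = 9 look like.**
- 0 to 1: item 1 turns positive (1 move).
- 0 to 2, 3, 4 or 5: both items turn positive (4 moves, one appearance).
- 1 to 2, 3, 4 or 5: item 2 turns positive (4 moves, one appearance).

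The nine visible worsenings reduce to three patterns, and none separates scores 2, 3, 4 and 5.

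**Step 4. Behaviour.** It is not an element of the table, so it produces no shift at any baseline.

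**Step 5. Dependence on the assumption.** If item 1 is negative at baseline and positive later while item 2 stays positive, a shift appears on item 1 only, without indicating that items 3 to 5 have changed. If item 1 goes from positive to negative, the table shows an apparent improvement on that item. A patient whose two items are both unchanged shows no shift, whatever items 3 to 5 do.

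**Step 6. What Table 14.3.6.5.2 adds.** One patient moving from 2 to 5 changes the mean of a fully assessed 60-patient arm by (5 − 2)/60 = 0.05. The same row shows a maximum observed score of 5 and a maximum change of at least +3, so that rise is visible. The row does not show how many patients rose: one patient at 5 and several at 5 give the same maximum. A rise from 2 to 3 is masked in the maximum observed score if another patient in that arm and visit scores 3 or more, and in the maximum change if another patient also rises by at least 1.

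**Step 7. Repeats.** SAP 6.3.1 allows one assessment per patient per time point in summaries and, after the first dose, takes the first of any repeated measurements. A worse repeat at a visit reaches only the listings.

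**Step 8. The same SAP on other safety data.** QTc is categorised by each patient's maximum post-baseline value and maximum change (6.3.16.4). Laboratory outliers get numbers and percentages of patients across scheduled and unscheduled tests (6.3.16.2). Lens opacity, the other EOCS category, is flagged directly from the LOCS III grades, and the Class I events have their own table (6.3.16.6).

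**The case against.** The strongest reply is that nothing goes uncaptured. Table 14.3.6.5.2 reports the maximum and the change from baseline, and both listings carry the detail. Protocol 11.3 and 11.3.1 require ideation and behaviour to be recorded as AEs, so they enter Table 14.3.1.2, which counts patients by arm. The treatment-emergent definition includes events present before treatment that increase in severity. EOCS have their own top-line table (14.3.2.2). The protocol asks only for a listing, so the SAP already goes further than required, and in a pilot of about 180 patients events can be counted by hand from the listings.

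Most of this stands. A reader might infer that a worsening patient is reported as unchanged throughout; that is true of the shift table only. A reader might also infer that the permissive *may* in SAP 6.1.3.8 weakens EOCS recording. The documents do not support that: SAP 6.1.3.1 says that events meeting the protocol definition will be recorded as EOCS, and the protocol governs what sites record. Nor does the SAP contradict the protocol.

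The reply does not supply a count based on the C-SSRS ratings. The AE and EOCS tables depend on investigator recording. Table 14.3.1.2 classifies by preferred term and by mild, moderate or severe, which are not C-SSRS categories. Rises to 3 or 4 fall below the score-5 or behaviour criterion that the SAP gives for an EOCS, so 2 to 3, 2 to 4 and 3 to 4 can be absent from both the shift table and the EOCS table. They would be counted by arm only if recorded as AEs.

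**Conclusion.** The point holds as a gap in presentation. Under the stated assumption about items 1 and 2, 6 of 15 possible worsenings show no shift, the remaining 9 are not graded above score 2, and new behaviour never appears. No table derived from the C-SSRS counts patients per arm with worsened ideation, by worst post-baseline category, or with behaviour. The 6 of 15 is a count of possible transitions. It says nothing about how many patients will make them, and the documents give no rates.

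The claim that safety events would be lost or concealed is not supported, for the reasons given above. The weight of the point is modest: a descriptive table that serves a primary safety objective is coarser than the score the SAP defines, and coarser than the SAP's own displays for QTc, laboratory outliers and lens events.

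**What to change.** Re-specify Table 14.3.6.5.1 as a shift from baseline ideation category (0 to 5) to worst post-baseline category, by arm. State that repeat and unscheduled assessments count towards the worst value, as an exception to the one-assessment rule in SAP 6.3.1.

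Add, per arm, the number and percentage of patients with:
- any worsening in ideation category;
- a post-baseline score of 4 or 5;
- any post-baseline suicidal behaviour.

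Derive the score-5 and behaviour events from the C-SSRS data, reconcile them with the recorded EOCS, and report any mismatch. Align the wording on EOCS recording in SAP 6.1.3.8 with SAP 6.1.3.1 and Protocol 11.3.

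The cost is one re-specified descriptive safety table and a reconciliation check. The data are already collected, and site procedures and patient management do not change.
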